7.1 Primary outcome

The principal analysis will be based on complete case data without imputation for those who dropped out of the study before the end of the 24 months. The primary outcome (SER at month 24) results from both eyes will be used and adjusted for baseline SER. The atropine and control groups will be compared using generalised estimating equations (GEE) and 95% confidence intervals (CIs), to allow for the correlation between eyes within a participant. Secondary analysis of the primary outcome will be adjusted for baseline SER, minimisation variables (i.e. site and ethnicity), baseline age and history of parental myopia (at least one parent).

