3.3 Data completion schedule

Participants will be followed every six months for a total of five trial visits as outlined in accordance with the schedule of assessments as shown in Table 1:

Doc No: ST06-RD01 Page **8** of **47**

Table 1: Schedule of Assessments for the CHAMP UK Study

	Baseline	6	12	18	24
		months	months	months	months
Consent	✓				
Randomisation	✓				
Medical history (including height*,					
weight*, concomitant medications	✓	✓	✓	✓	✓
and spectacle correction)					
Severity of parental myopia (self-	√				
report)	ŕ				
Adverse events		✓	✓	✓	✓
Tolerability		✓	✓	✓	✓
EQ-5D-Y questionnaire	✓	✓	✓	✓	✓
Activities questionnaire- to be sent	✓	✓	✓	✓	✓
home with participant for completion					
Best corrected VA (logMAR ETDRS)	✓	✓	√	√	✓
Near VA (near logMAR ETDRS)	✓	✓	✓	✓	✓
Iris colour	✓				
Reading speed (Wilkins Rate of Reading Test)	✓	✓	✓	✓	✓
Pupil diameter prior to cycloplegia	✓	✓	✓	✓	✓
Accommodation (in accordance with guideline)*	✓	✓	✓	✓	✓
Peripheral retinal defocus (autorefractor)*	✓		✓		✓
Anterior chamber depth (laser biometer)*	✓		✓		✓
Cycloplegic refractive error (autorefractor)	✓	✓	✓	✓	✓
Ciliary body biometry (AS-OCT)*	✓		✓		✓
Central axial length (laser biometer)	✓	✓	✓	✓	✓
Peripheral axial length (laser biometer)*	✓		✓		✓
Chorio-retinal thickness (SD-OCT)*	✓	✓	✓	✓	✓
MEMS data		✓	√	√	✓
Study drug dispensing	✓	✓	✓	✓	

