5. SAMPLE SIZE CALCULATIONS

We anticipate that the effect of atropine eye drops in a UK population will be smaller than the reported effect in Chinese populations, but assuming that atropine reduces the progression of myopia by at least 40% in 24 months from a control mean of -0.8D7 (40% of 0.8 is equivalent to a mean difference of -0.32D between intervention and control group at 24 months), using SD=0.7D, a correlation (interclass correlation coefficient) between eyes of 0.9 and a variation inflation factor of 1.9, we will need 97 participants in each group. Considering a dropout rate of 15% and that 10% of the recruited children will be Chinese, we will need a total of 289 participants: 193 atropine, 96 placebo (152 atropine, 76 placebo inflated by a variance inflation factor of 1.9) to detect this difference in the non-Chinese population with 90% power.

Justification: In a study of 400 Chinese children evaluating the effect of 24 months of 1% atropine eye drops, myopia progression was -1.20 +/- 0.69 D in the placebo control group, and -0.28 +/- 0.92 D in the atropine group. We have assumed that progression of myopia and efficacy of atropine will be less in UK children than in Chinese children2.

Progression of myopia of untreated children was estimated from the control groups of randomized controlled trials for myopia. The following progression data have been reported:

- Katz 2003⁴ (Chinese race): progression of -1.28D (SD 0.78) D after 2 years (control was spectacles)
- Edwards 2002⁵ (Chinese race): progression of -1.26D (SD 0.74) D after 2 years (control was single vision lenses)
- Chua 2006³, ATOM study (Chinese race): progression of -1.20D (SD 0.69) after 2 years (control was placebo drops)
- Hyman 2005⁶, COMET trial (children of mixed races, with whites being the most common ethnicity): progression of 1.32D after 3 years (standard error 0.04) (control was single vision lenses)
- Breslin 2013⁷, In an observational study from the UK, myopia progression was 1.14D after 3 years.

Doc No: ST06-RD01 Page **12** of **47**

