7.5 Additional analyses

Additional analyses will be performed on the primary and secondary outcomes to investigate any differences between atropine and placebo groups at all other available time points not previously analysed (i.e. 6, 12 and 18 months). The primary and secondary outcomes at baseline will only be presented by treatment arm in the PP analysis in this additional analyses, as the ITT baseline results are presented in the baseline characteristics table.

For the primary outcome SER, results will be used from both eyes and will be compared using GEE (repeated measures model) and 95% CIs and will be adjusted for baseline SER. Secondary analysis of the primary outcome will be adjusted for baseline SER and minimisation variables (i.e. site and ethnicity), baseline age and history of parental myopia (at least one parent).

For the secondary outcome analyses, results will be used from both eyes to investigate if atropine has an effect on the following endpoints; central axial length, pupil diameter, uniocular BCdVA and uniocular near VA. These endpoints will be compared between the two groups using GEE (repeated measures model) and 95% CIs and will be adjusted for the corresponding baseline secondary outcomes (if available). For the following endpoints; binocular BCdVA, binocular near VA, reading speed and quality of life (i.e. EQ-5D-Y VAS and Index) comparisons between the two groups will be performed using repeated measures ANCOVA and 95% CIs and will be adjusted for the corresponding baseline secondary outcome (if available).

Tolerability will be compared between the atropine and placebo groups using repeated measures ANOVA and 95% CI. Spectacle correction will be compared between the atropine and placebo groups using repeated measures generalised linear model. N(%) of spectacle correction (all day and sometimes) will also be presented by treatment arm.

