7.6 Missing data

Sensitivity analyses will be undertaken to assess the impact of missing data for the primary outcome, by imputing extreme values of change within treatment arm (i.e. smallest and largest change from the previous time point to 24 months). Results between the atropine and placebo groups will be compared using GEE and 95% CIs and will be adjusted for baseline SER and also adjusted for baseline SER, minimisation variables (i.e site and ethnicity), baseline age and history of parental myopia (at least one parent). If the baseline primary outcome is missing, spectacle refraction based on the current prescription at baseline will be used in the sensitivity analysis.

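### The primary analysis uses month-24 SER in complete cases only, so the 6-, 12- and 18-month SER of children who drop out never informs the primary estimate

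*Supplement*

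**What the plan says.** - **Analysis set (SAP 7.1).** "The principal analysis will be based on complete case data without imputation for those who dropped out of the study" before month 24.
- **Model (SAP 7.1).** "The primary outcome (SER at month 24) results from both eyes will be used and adjusted for baseline SER". GEE is there "to allow for the correlation between eyes within a participant"; it links the two eyes, not the visits. The secondary analysis of the primary outcome adds site, ethnicity, age and parental myopia, but no interim SER.
- **Measurement (SAP 3.3, Table 1).** The row "Cycloplegic refractive error (autorefractor") is ticked at baseline, 6, 12, 18 and 24 months.
- **Where interim SER is used (SAP 7.5, 8.8).** A repeated-measures GEE compares the arms "at all other available time points not previously analysed (i.e. 6, 12 and 18 months"), so month 24 is outside it.
- **Missing data (SAP 7.6).** The sensitivity analysis works "by imputing extreme values of change within treatment arm (i.e. smallest and largest change from the previous time point to 24 months").
- **Expected dropout.** Section 5 reads "Considering a dropout rate of 15" per cent, whereas section 3.4 expects little missing data.

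**The concern.** A child seen at 6, 12 and 18 months but not at 24 contributes nothing to the primary estimate. That estimate is safe if, within each arm, leaving is unrelated to month-24 SER once baseline SER is known. Progression already recorded at earlier visits is the obvious predictor of month-24 SER, and it is also something that could prompt a family to leave. If fast progressors leave mainly from placebo, the completers flatter placebo and the estimated benefit shrinks. If they leave mainly from atropine, the benefit is overstated.

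No planned analysis uses the interim values to correct for this at month 24. The SAP already applies repeated-measures GEE to exploratory outcomes with month 24 included (7.3 and the exploratory table), so its primary outcome draws on less of the available data at its key visit than those outcomes do.

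**Working it through.** **1. How many children are affected.** Inputs from section 5: difference 0.32 D (40% of 0.8 D), SD 0.7 D, between-eye correlation 0.9, inflation factor 1.9, 90% power, 2:1 allocation, 15% dropout, 10% Chinese. Two-sided 5% is assumed, since section 7 gives only p<0.05.

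- Placebo eyes: (1 + 1/2) × (1.960 + 1.282)² × 0.7² / 0.32² = 75.4, so 76. Atropine eyes: 152. Both match the plan.
- Children: 76 × 1.9/2 = 72.2 and 152 × 1.9/2 = 144.4, together 216.6.
- Allowance: 216.6 / (1 − 0.15 − 0.10) = 288.8, so 289 as stated.
- Children allowed to be without a month-24 value: 0.15 × 289 ≈ 43.

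**2. What dropout does to the complete-case estimate.** Simulation: 1,500 trials of 289 children, 2:1, true benefit 0.32 D, placebo progression 0.8 D over 24 months. The SD of the child mean of two eyes is 0.7 × √0.95 = 0.682 D (variance 0.4655). Assumptions not in the documents: linear random-slope progression, visit noise SD 0.2 D, and logistic dropout depending on the last observed progression at 2 log-odds per D. The comparison is of mean change; baseline SER is not modelled. The all-visit estimate uses sequential regressions on earlier visits within arm, which is maximum likelihood for monotone dropout.

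| Dropout mechanism | Complete case, 15% | All visits, 15% | Complete case, 25% | All visits, 25% |
|---|---|---|---|---|
| Completely random | 0.318 | 0.318 | 0.317 | 0.318 |
| Fast progressors leave, same rule in both arms | 0.303 | 0.324 | 0.288 | 0.319 |
| Depends on progression in placebo only | 0.245 | 0.320 | 0.198 | 0.317 |
| Opposite directions by arm | 0.191 | 0.321 | 0.104 | 0.317 |

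Attenuation at 15%: 1 − 0.303/0.32 = 5%; 1 − 0.245/0.32 = 23%; 1 − 0.191/0.32 = 40%.

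**3. Weaker dependence** (log-odds 0.7 or 1.0 per 1 D per two years of faster progression, 15% dropout).

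- Placebo only: 0.271 to 0.279 D at 0.7 and 0.256 to 0.265 D at 1.0 across repeated simulations. Attenuation runs from 1 − 0.279/0.32 = 13% to 1 − 0.256/0.32 = 20%.
- Same rule in both arms: 0.308 and 0.305 D, that is 4 to 5%.
- Same slope with dropout fixed at 15% in each arm: 0.319 D at both values, essentially no bias, because both arms lose the same part of the distribution.

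**4. Precision under random dropout.** SE 0.0919 complete case against 0.0862 with all visits: 1 − 0.0862/0.0919 = 6% smaller. A second simulation gave 0.092 against 0.089, or 3%.

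**5. Whether section 7.6 fills the gap.** It was read as the last observed value plus the smallest or largest change in the child's own arm. With placebo-only dependence and 15% dropout:

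| Log-odds | Complete case | The two 7.6 analyses | Regression imputation from interim SER |
|---|---|---|---|
| 0.7 | 0.276 | 0.305 and 0.287 | 0.323 |
| 1.0 | 0.256 | 0.301 and 0.274 | 0.319 |

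Both 7.6 results lie below 0.32 D, so the pair need not bracket the true effect. Each run applies the same type of extreme to both arms and carries no imputation uncertainty.

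**The case against.** The strongest reply is masking. Section 6.2 has identical bottles, so families see progression but not allocation, and the natural mechanism is one rule acting in both arms. Under that rule the loss is about 5% or less at 15% dropout, with power of 92 to 93% against 93% under random dropout in the same simulation. This stands, and it makes the larger figures conditional. Differences in tolerability could still make dropout differ by arm, but the documents give no data on that.

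Other parts also stand:

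- A reader might infer that the complete-case analysis is biased as it is. The documents do not support that: they give no dropout mechanism, and the 15% is a sample-size allowance.
- A reader might infer that power falls from 94% to 81%. The lower figure needs placebo-only dependence. The 94% counts all 289 children, whereas section 5 claims 90% for the non-Chinese population, so this is not a fall from design power.
- A reader might infer that the interim data are thrown away. They are analysed in 7.5, and 7.6 starts from the previous visit. They are lost to the primary estimate, not to the trial.
- A reader might infer that the intention-to-treat label is wrong. In the text available the definition in section 4 breaks off, so this cannot be checked.
- The all-visit analysis recovers 0.32 D because dropout was simulated from observed progression. If dropout followed unobserved progression, that analysis would be biased too.

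Withdrawals are tabulated by arm and reason (8.4), so differential dropout would be visible. Seeing it would not correct the estimate.

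**Conclusion.** The point holds as a conditional weakness with an inexpensive repair. About 43 of 289 children may lack a month-24 value, and no planned analysis uses their interim SER to give a month-24 estimate under missing at random.

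With 15% dropout and the assumed random slopes, the bias is nil to about 5% if one mechanism acts in both arms. It is about 13 to 23% only if progression drives dropout in placebo alone, and larger (about 40%) if the dependence runs in opposite directions by arm. Sign and size rest on assumptions outside the documents. The efficiency gain of about 3 to 6% in SE does not need outcome-related dropout, but it is small.

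The case for change is that the data are already collected and that missing at random given baseline and interim SER is a weaker assumption than the one complete case needs.

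**What to change.** Make the primary estimate use all randomised children with any SER, by one of two routes:

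- **Multiple imputation.** Impute month-24 SER separately by arm from baseline, 6-, 12- and 18-month SER of both eyes, then run the planned GEE and combine the results.
- **Mixed model.** Fit a likelihood-based model to all four follow-up visits, with arm by visit, baseline SER by visit and eye within child, and report the month-24 contrast.

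Adding month 24 to the unweighted GEE of 7.5 is not enough, because that model in general needs data missing completely at random given its covariates. Keep complete case and the 7.6 extreme-change imputations as sensitivity analyses.

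The cost is SAP wording and modest programming, with no new data. The remaining limit is reliance on missing at random, which does not protect against dropout driven by progression that no visit recorded.

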6. RANDOMISATION AND BLINDING

6.1 Randomisation

All participants who agree to join the study will be assigned a unique Participant Identification Number. Eligible participants will be randomised using a 2:1 allocation ration into the two groups (193 atropine: 96 placebo). Randomisation will use the remote automated computer randomisation application, Sealed Envelope, ensuring allocation concealment. Randomisation will be computer-allocated using a minimisation algorithm to ensure balanced allocation of participants across the two treatment groups. Minimisation will be by centre, ethnic background (white/non-white), and severity of myopia (less than - 3D in either eye / -3D or greater in the eye with more severe myopia). The unit of randomisation will be the participant (not the eye).

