Doc No: ST06-RD01 Page **13** of **47**

7. **ANALYSIS PRINCIPLES**

Baseline characteristics and follow up measurements will be summarised as mean and standard deviation (SD), median and inter-quartile range (IQR) or numbers and frequencies (%) as appropriate, depending on the scale of measurement and distribution. Analysis will be based on both the intention to treat (ITT) principle and per protocol (PP) analysis. PP analysis will explore results in those who had at least 80% adherence to the study drug. A p-value <0.05 will be considered as statistically significant.

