8.5 Trial Outcomes

Primary efficacy outcome:

 SER at month 24: mean (SD) by treatment arm, difference in means with 95% CI, p-value from GEE model, adjusted for baseline SER in ITT analysis and PP analysis.

Secondary analysis of the primary efficacy outcome:

- SER at month 24: mean (SD) by treatment arm, difference in means with 95% CI, p-value from GEE model, adjusted for baseline SER, minimisation variables (i.e. site and ethnicity), baseline age and history of parental myopia (at least one parent), in ITT analysis and PP analysis.
- Uniocular (BCdVA) at month 24: mean (SD) by treatment arm, difference in means with 95% CI, p-value from GEE, adjusted for baseline uniocular BCdVA in ITT and PP analysis.
- Binocular BCdVA at month 24: mean (SD) by treatment arm, difference in means with 95% CI,
 p-value from ANCOVA, adjusted for baseline BCdVA in ITT and PP analysis.
- Central axial length at month 24: mean (SD) by treatment arm, difference in means with 95% CI,
 p-value from GEE, adjusted for baseline central axial length in ITT and PP analysis.
- Uniocular near VA at month 24: mean (SD) by treatment arm, difference in means with 95% CI, p-value from GEE, adjusted for baseline uniocular near VA in ITT and PP analysis.
- Binocular near VA at month 24: mean (SD) by treatment arm, difference in means with 95% CI, p-value from ANCOVA, adjusted for baseline binocular near VA in in ITT and PP analysis..
- Pupil diameter at month 24: mean (SD) by treatment arm, difference in means with 95% CI, p-value from GEE, adjusted for baseline pupil diameter in ITT and PP analysis.
- Spectacle correction at month 24: no. (%) by treatment arm, risk difference and p-value from from chi-square test in ITT and PP analysis.
- Frequency of spectacle correction at month 24 (all day and sometimes): no. (%) by treatment arm in ITT and PP analysis.
- EQ-5D-Y VAS at month 24: mean (SD) by treatment arm, difference in means with 95% CI, p-value from ANCOVA, adjusted for baseline EQ-5D-Y VAS in intention to treat analysis and per protocol analysis.
- EQ-5D-Y Index score at month 24: mean (SD) by treatment arm, difference in means with 95% CI, p-value from ANCOVA, adjusted for baseline EQ-5D-Y index in ITT and PP analysis.
- Tolerability eye feels at month 24: mean (SD) by treatment arm, difference in means with 95% CI, p-value from independent t-test, in ITT and PP analysis.

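### The primary model omits centre and ethnicity, on which allocation is minimised, so its confidence interval is somewhat too wide if they are prognostic

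*Supplement*

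**What the plan says.** SAP Section 6.1 (Randomisation): "Minimisation will be by centre, ethnic background (white/non-white), and severity of myopia". The child is randomised, not the eye, in a 2:1 ratio.

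Section 7.1 (Primary outcome): "The primary outcome (SER at month 24) results from both eyes will be used and adjusted for baseline SER". Section 8.5 repeats this for reporting: "p-value from GEE model, adjusted for baseline SER in ITT analysis and PP analysis". Section 7 sets the threshold: "A p-value <0.05 will be considered as statistically significant".

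Section 7.1 also pre-specifies a secondary analysis of the same outcome, which adds site, ethnicity, baseline age and parental myopia. It recurs in Sections 7.5, 7.6, 8.5, 8.6 and 8.8 and has its own column in the main results table of Appendix 1. The SAP gives no reason for making the less adjusted model the primary one.

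Section 5 holds the planning figures. The target effect is stated as "40% of 0.8 is equivalent to a mean difference of -0.32D between intervention and control group at 24 months". The variance inputs are an SD of 0.7 D, an inter-eye correlation of 0.9 and an inflation factor of 1.9. The resulting total of 289 is meant "to detect this difference in the non-Chinese population with 90% power". It assumes slower progression in UK children than in Chinese children, with controls at -0.8 D against -1.20 D over 24 months.

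**The concern.** Minimisation makes the arms alike on centre and ethnicity, so differences between centres or ethnic groups add little to the real sampling error of the treatment contrast. A model without these terms leaves their variation in the residual and computes its standard error as if the arms could differ on them by chance. The reported standard error is then larger than the true one. A robust GEE variance does not correct this. The primary interval over-covers and the primary test rejects less often than 5% under the null.

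Severity, the third factor, is dealt with through continuous baseline SER. Age is a separate matter. It is not balanced by design, so a model without it has a correct standard error that is simply larger than it need be.

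At stake are the precision and power of the headline result. The plan itself treats these variables as relevant: ethnicity and age are subgroup factors in Section 7.4 and covariates in the secondary model.

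**Working it through.** **1. Reproduce the plan's sample size.** Inputs from Section 5 and Section 7: difference 0.32 D, SD 0.7 D, two-sided alpha 0.05, power 90%, 2:1 allocation, inflation factor 1.9, dropout 15%, Chinese share 10%.
- Eyes needed: 76 placebo and 152 atropine, as stated.
- Participants: (152 + 76) × 1.9 / 2 = 216.6 evaluable.
- Recruited: 216.6 / (1 − 0.15 − 0.10) = 288.8, that is 289.
- Equal allocation: 102 eyes per arm × 1.9 / 2 = 96.9, that is 97.

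**2. Standard error of the planned analysis.**
- SD of a child's two-eye mean: 0.7 × √(1.9/2) = 0.682 D.
- SE = 0.682 × √(1/144.4 + 1/72.2) = 0.0983 D, so the CI half-width is 1.96 × 0.0983 = 0.193 D.
- Power at 0.32 D: Φ(0.32/0.0983 − 1.96) = 90.2%.

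This takes 0.7 D as the SD left after baseline SER.

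**3. Effect of the omitted covariates.** Let R²m be the share of that residual variance explained by the minimised factors (centre, ethnicity) and R²a the further share explained by age. Relative to the SE that the SER-only model reports:
- true SE of the SER-only estimate: √(1 − R²m)
- SE of the adjusted model: √(1 − R²m − R²a)

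So the total share sets how much wider the primary CI is, but only R²m lowers alpha: true alpha = 2 × [1 − Φ(1.96/√(1 − R²m))].

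**4. What the SAP's own figures imply for ethnicity.** R² = 0.1 × 0.9 × 0.4² / 0.7² = 0.0144 / 0.49 = 2.9%. Here 0.4 D is 1.20 − 0.8. The CI ratio is 1/√(1 − 0.029) = 1.015. The minimised factor is white/non-white, whose split the SAP does not give. If every non-white child showed the 0.4 D difference, shares of 20% to 50% would give 5% to 8%.

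**5. Assumed range.** The last three columns suppose that centre and ethnicity supply the whole share.

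| R² | CI wider by | True alpha, SER-only | Power, SER-only | Power, adjusted |
|---|---|---|---|---|
| 0 | 0 | 5.0% | 90.2% | 90.2% |
| 3% | 1.5% | 4.7% | 90.6% | 91.1% |
| 5% | 2.6% | 4.4% | 90.8% | 91.6% |
| 10% | 5.4% | 3.9% | 91.4% | 92.9% |
| 20% | 11.8% | 2.8% | 92.6% | 95.3% |

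If a 10% total were half age, the CI would still be 5.4% wider, but alpha would be 4.4% rather than 3.9%.

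**6. Simulation of the mechanism.** 1,500 runs per setting with 2:1 minimisation, a two-eye mean outcome and robust standard errors. Assumed: 246 children, five centres, 30% non-white.

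| R² centre / ethnicity / age | True SE, SER-only | Mean reported SE | Type I error | CI ratio to adjusted |
|---|---|---|---|---|
| 0 / 0 / 0 | 0.0917 | 0.0920 | 4.7% | 0.997 |
| 2% / 3% / 5% | 0.0892 | 0.0919 | 4.7% | 1.050 |
| 5% / 5% / 5% | 0.0869 | 0.0919 | 3.8% | 1.081 |
| 5% / 5% / 10% | 0.0892 | 0.0920 | 4.5% | 1.115 |
| 10% / 10% / 0 | 0.0842 | 0.0923 | 3.1% | 1.116 |

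Monte Carlo error on the type I rates is about √(0.05 × 0.95/1500) = 0.6 percentage points, so the SE columns are the firmer evidence. The direction agrees with the formula. With no prognostic value, the adjusted interval is only 0.3% wider.

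**The case against.** The strongest reply is that the plan already contains the fuller model. It is pre-specified and sits beside the primary result in the main table. A reader might therefore infer too much from this point, namely that the trial ignores data it collects. The SAP does not support that: site, ethnicity, age and parental myopia are all used, though not in the analysis that supplies the primary interval and p-value. That last part stands, because a secondary column does not change the headline.

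Second, Section 2.1 defines the primary outcome as adjusted for baseline, and the primary model follows that definition. True, but the definition does not exclude further covariates.

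Third, the size is uncertain. No R², centre effect or non-white share is given. The 0.4 D difference is Chinese versus UK, and applying it to all non-white children is an assumption. If only Chinese children differ, a white/non-white term could capture less than 2.9%. This stands, and it is why the figures are a range that starts at no gain.

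Fourth, the 216.6 evaluable children are the non-Chinese set, from which the Chinese contrast is absent, whereas Section 7.1 analyses all complete cases: 289 × 0.85 = about 246, with SE about 0.0925 and power at 0.32 D about 93% before any added covariate. This also stands. It lowers the stakes for power, but the CI ratios and alpha depend only on R², not on the number of children.

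Two further readings are tempting and wrong. The omission does not bias the estimate or inflate false positives, since the error is conservative. And age does not belong in the coverage argument, because it is not a minimisation factor.

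**Conclusion.** The point holds in a limited form. The primary GEE leaves out two factors that minimisation balances. If they are prognostic, its standard error is overstated, its interval somewhat too wide and its type I error below 5%. Omitting baseline age adds a loss of precision with coverage intact.

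On the SAP's own figures for Chinese children, the interval is about 1.5% too wide and alpha about 4.7%. If the covariates explain an assumed 5–20%, the interval is about 3–12% too wide. Alpha of 4.4% to 2.8% requires all of that share to come from centre and ethnicity. In that case power at 0.32 D rises from 90.8% to 91.6% (R² 5%) or from 92.6% to 95.3% (R² 20%), so the SER-only model already meets the planned 90%.

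The case for change is that the analysis should match the allocation and that doing so is nearly free. It does not rest on the trial being invalid or underpowered as planned.

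**What to change.** In Sections 7.1 and 8.5, make the primary GEE: month-24 SER on arm, same-eye baseline SER, centre, ethnicity (white/non-white) and baseline age, clustered on participant. Report the SER-only model as supportive.

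Keep parental myopia in the secondary model. The baseline table in Appendix 1 has a category for unknown parental history, and children in it could drop out of a complete-case fit.

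Use the same covariates in the per-protocol, sensitivity and subgroup models, and update the table footnotes.

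The cost is SAP wording and a small change to the model, with no new data: all the variables are recorded at or before randomisation. The SAP cites protocol version 5.0, which was not among the documents reviewed. If the protocol fixes the primary model, its wording must be aligned as well.
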